### 9.5.2.2 Laboratory data

Laboratory data for two groups of tests (hematology and chemical chemistry) will be summarized by presenting shift tables using extended normal ranges with thresholds representing clinical relevant abnormality and by presenting descriptive statistics of raw data and change from Baseline (Day1). Values outside the extended normal range will be listed by patient and treatment arm and flagged in data listings.

### **9.5.2.3 Vital signs**

Vital signs will be summarized by presenting shift tables using thresholds representing clinical relevant abnormality ([Appendix 1](#)) and by presenting descriptive statistics of raw data and change from Baseline (Day1). Values outside the extended normal range will be listed by patient and treatment arm and flagged in data listings.

### **9.5.2.4 Ocular assessments**

Ocular assessments (including IOP) will be summarized descriptively by time point and treatment group based on the safety set. Intraocular pressure changes (pre-injection) from Baseline (Day1) by visit and changes from before dosing to after dosing within a visit will be descriptively summarized.

Summaries will be presented separately for the study eye only and for the fellow treated eye.

### **9.5.3 Resource utilization**

Not applicable.

### **9.5.4 Pharmacokinetics**

Not applicable.

### **9.5.5 DNA**

[figure not shown]
Not applicable.

### **9.5.6 Biomarkers**

Not applicable.

### **9.5.7 PK/PD**

Not applicable.

## **9.7 Interim analyses**

Not applicable.

## **9.8 Sample size calculation**

In order to detect a clinically meaningful difference in the number of injections (at least 2 injections) at Month 11, as suggested by the principal investigators, this study will randomize at least 56 patients (28 per arm).

For the sample size calculation, we will assume a difference between arms of 2 injections and a standard deviation (SD) of 2.32 (based on CAVNAV study (Liegler et al. 2014)). Based on the non-parametric Wilcoxon-Mann Whitney test for the difference in means this would require 25 patients per arm with 80% power and a 0.025 significance level (1sided), however assuming approximate 10% drops out rate, a total of at least 56 patients (28 per arm) are required to be randomized.

Approximately 70 patients will need to be screened in order to have at least 56 patients eligible and commencing treatment in the trial.

All sample size calculations performed using EAST 6.0.

## **10 Ethical considerations**

### **10.1 Regulatory and ethical compliance**

This clinical study was designed and shall be implemented, executed and reported in accordance with the ICH Harmonized Tripartite Guidelines for Good Clinical Practice, with applicable local regulations (including European Directive 2001/20/EC, US CFR 21, and

Japanese Ministry of Health, Labor, and Welfare), and with the ethical principles laid down in the Declaration of Helsinki.

## **10.2 Informed consent procedures**

Eligible patients may only be included in the study after providing written (witnessed, where required by law or regulation), IRB/IEC-approved informed consent or if applicable, after such consent has been provided by a legally acceptable representative of the patient.

In cases where the patient's legally acceptable representative (LAR) gives consent, the patient should be informed about the study to the extent possible given his/her understanding. Informed consent must be obtained before conducting any study-specific procedures (i.e. all of the procedures described in the protocol).

The process of obtaining informed consent should be documented in the patient source documents.

Novartis will provide to investigators in a separate document a proposed informed consent form that complies with the ICH GCP guideline and regulatory requirements and is considered appropriate for this study. Any changes to the proposed consent form suggested by the investigator must be agreed to by Novartis before submission to the IRB/IEC and a copy of the approved version must be provided to the Novartis monitor after IRB/IEC approval.

Women of child bearing potential should be informed that taking the study drug may involve unknown risks to the fetus if pregnancy were to occur during the study and agree that in order to participate in the study they must adhere to the contraception requirement for the duration of the study. If there is any question that the patient will not reliably comply, they should not be entered in the study.

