Stop study participation	Point/time at which the patient came in for a final evaluation visit or when study/investigational treatment was discontinued whichever is later.
Study drug	Any drug administered to the patient or therapeutic procedure as part of the required study procedures; includes investigational drug and any control drugs or therapeutic procedure.

Study eye	The study eye is the eye selected by the investigator at Baseline (according to the protocol) to receive the study treatment.
Study treatment discontinuation	Point/time when patient permanently stops taking study treatment for any reason; may or may not also be the point/time of premature patient withdrawal.
Variable	Information used in the data analysis; derived directly or indirectly from data collected using specified assessments at specified time points.

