## **Post-treatment Follow-up Period: Month 11 to Month 12**

The last study assessment will be performed at Month 12, i.e., 1 month after the last possible ranibizumab injection/laser treatment in this study.

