#### Exclusion criteria for patient

1. Inability to comply with study or follow-up procedures
2. Women of child-bearing potential, defined as all women physiologically capable of becoming pregnant, unless they are using effective methods of contraception during dosing study treatment. Effective contraception methods include:

- Total abstinence (when this is in line with the preferred and usual lifestyle of the patient). Periodic abstinence (e.g., calendar, ovulation, symptothermal, post-ovulation methods) and withdrawal are not acceptable methods of contraception.
- Female sterilization (have had surgical bilateral oophorectomy with or without hysterectomy) or tubal ligation at least six weeks before taking study treatment. In case of oophorectomy alone, only when the reproductive status of the woman has been confirmed by follow up hormone level assessment.
- Male sterilization (at least 6 m prior to screening). For female subjects on the study, the vasectomized male partner should be the sole partner for that subject.
- Barrier methods of contraception: Condom or Occlusive cap (diaphragm cervical/vault caps) with spermicidal foam/gel/film/cream/ vaginal suppository.
- Use of oral, injected or implanted hormonal methods of contraception or other forms of hormonal contraception that have comparable efficacy (failure rate <1%), e.g., hormone vaginal ring or transdermal hormone contraception.
- Placement of an intrauterine device (IUD) or intrauterine system (IUS).

In case of use of oral contraception women should have been stable on the same pill for a minimum of 3 months before taking study treatment.

Reliable contraception should be maintained throughout the study and for 3 months after study treatment discontinuation.

Women are considered post-menopausal and not of childbearing potential if they have had 12 months of natural (spontaneous) amenorrhea with an appropriate clinical profile (e.g., age appropriate, history of vasomotor symptoms) or have had surgical bilateral oophorectomy (with or without hysterectomy) or bilateral tubal ligation at least 6 weeks ago. In the case of oophorectomy alone, only when the reproductive status of the woman has been confirmed by follow-up hormone level assessment is she considered not of childbearing potential.

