## **6 Visit schedule and assessments**

[Table 6-1](#) lists all of the assessments and procedures to be performed by study visits.

All data obtained from these assessments must be supported in the patient's source documentation. Assessments are indicated with an "X" when they need to be performed.

A planned study visit schedule will be established at the time of Baseline (Day 1) for all patients. Study assessments will be performed at Screening, Baseline (Day1), and at monthly visits (defined as every 30 days calculated from Baseline (Day1)) from Month 1 through Month 12,  $\pm$  7 days to allow for flexibility in scheduling. Ranibizumab should be administered in the study eye on the day of the study visit. Only when ranibizumab and laser photocoagulation are not to be applied on the same day to the same eye, laser treatment can be deferred for up to 14 days relative to the ranibizumab treatment. In the other case, study treatment has to occur within the visit window as specified in [Table 6-1](#).

Should a deviation from the study visit schedule occur, all efforts should be made to return to the planned visit schedule.

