- i. Tonometry: In the study eye, tonometry is conducted at every study visit in all treatment arms to assess IOP, regardless of treatment administration afterwards. On visits when ranibizumab and/or laser treatment is administered, also post-injection tonometry should be performed between 15 and 60 minutes after treatment in the study eye. In the fellow untreated eye, tonometry will be conducted at Screening, Baseline (Day 1), Month 6, and the EOS visit.

- k. These assessments are optional if the investigator requires the respective information to assess the need for retreatment.
- l. Before the study treatment with ranibizumab, ensure that patients have self-administered their antimicrobials 4 times daily for 3 days before each scheduled study treatment and instruct patients to self-administer their antimicrobials again 4 times daily for 3 days post-treatment with ranibizumab.
- m. In Arm 2, the first laser treatment must be given to the target within vascular arcades as soon as indicated, but can be deferred by a maximum of 14 days relative to the ranibizumab injection.
- n. Post injection safety after ranibizumab and/or laser treatment, comprising: central artery perfusion, vision check, IOP. (Perform finger count, hand motion, and light perception (when indicated) within 15 minutes post-treatment for the study eye only).
- o. Follow-up Contact: Contact the patient by telephone for safety evaluations 2 ( $\pm$  1) days following each study visit when study treatment (ranibizumab and/or laser photocoagulation) is administered.
- p. EOS: For patients, who complete, withdraw or are discontinued early (refer to [Section 5.6.2](#)) from the study, perform 30 days (+ 7 days) following the last study treatment or the last study visit.

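### Section 10.2 ends the contraception commitment with the study, although exclusion criterion 2 requires it for 3 months after treatment stops; after a Month 11 treatment this is about 53 to 60 days too early

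*Protocol*

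**What the plan says.** The protocol states the contraception period in three places, each time differently.

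- Section 10.2 (Informed consent procedures), on what women of childbearing potential are told and agree to: "they must adhere to the contraception requirement for the duration of the study". The risk described in the same sentence is likewise confined to pregnancy arising while the study is running.
- Section 4.2, exclusion criterion 2, opening clause: women of childbearing potential are excluded "unless they are using effective methods of contraception during dosing study treatment".
- Section 4.2, exclusion criterion 2, duration sentence: "Reliable contraception should be maintained throughout the study and for 3 months after study treatment discontinuation".

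The Glossary defines study treatment discontinuation as "Point/time when patient permanently stops taking study treatment for any reason", so the 3 months run from the last treatment and not from the last visit.

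The schedule fixes how far apart those two points are. Section 3.1 states: "The last study assessment will be performed at Month 12, i.e., 1 month after the last possible ranibizumab injection/laser treatment in this study". Footnote p of Table 6-1 tells sites to hold the end-of-study visit as follows: "perform 30 days (+ 7 days) following the last study treatment or the last study visit". Section 5.6.1 plans no extension.

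**The concern.** Section 10.2 and criterion 2 agree on the end date only if the last treatment falls about 3 months before the study ends. Dosing is as needed at monthly visits up to Month 11, so a late last treatment is an ordinary possibility. When that happens, a woman who does exactly what Section 10.2 describes may stop contraception while criterion 2 still requires it.

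Section 10.2 gives the reason for the rule itself: the risk to a fetus is unknown. What it omits is the post-treatment part of that safeguard. The last scheduled pregnancy test is at the end-of-study visit (Section 6.5.6), so no scheduled test falls in the omitted weeks, and the safeguard then depends on the woman knowing her obligation.

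**Working it through.** Only day arithmetic is needed.

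**Inputs**

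- Study month: Section 6 sets "monthly visits (defined as every 30 days calculated from Baseline (Day1)) from Month 1 through Month 12", so Month 9 is Day 270, Month 10 is Day 300, Month 11 is Day 330 and Month 12 is Day 360 (also the days shown in Table 6-1).
- Last possible treatment: Month 11, Day 330 (Section 3.1).
- End-of-study visit: 30 to 37 days after the last treatment or last visit (Table 6-1, footnote p).
- Contraception after the last treatment: 3 months (Section 4.2, criterion 2). I take this as 3 × 30 = 90 days; the protocol does not give it in days.

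**The protocol's own figure.** Month 12 minus Month 11 is 360 − 330 = 30 days, which reproduces the 1 month stated in Section 3.1.

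**Last treatment at Month 11**

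- End under criterion 2: 330 + 90 = Day 420.
- End under Section 10.2: 330 + 30 = Day 360 to 330 + 37 = Day 367.
- Shortfall: 420 − 367 = 53 days to 420 − 360 = 60 days. Equivalently, 90 − 37 = 53 and 90 − 30 = 60.

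**Earlier last treatment, woman completes the study at Day 360**

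| Last treatment | Criterion 2 ends | Study ends | Shortfall |
|---|---|---|---|
| Month 11 (Day 330) | Day 420 | Day 360 | 60 days |
| Month 10 (Day 300) | Day 390 | Day 360 | 30 days |
| Month 9 (Day 270) | Day 360 | Day 360 | 0 days |

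The shortfall is therefore nominally zero for any completer last treated on or before Day 360 − 90 = Day 270.

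**Early withdrawal.** If the end-of-study visit is counted from the last treatment, the interval is again 30 to 37 days and the shortfall again 53 to 60 days, whatever the month. If it is counted from a later study visit, the shortfall is smaller.

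**Sensitivity to the assumptions**

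- Calendar months, 89 to 92 days: 89 − 37 = 52 to 92 − 30 = 62 days.
- The ±7-day windows of Table 6-1 applied independently at Month 11 and Month 12, instead of footnote p: the interval is 30 − 14 = 16 to 30 + 14 = 44 days, and the shortfall is 90 − 44 = 46 to 90 − 16 = 74 days.

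**The case against.** The best defence is that Section 10.2 sets no rule of its own. It refers to a contraception requirement defined elsewhere, which can only be criterion 2, and criterion 2 has the 3 months right. A woman who follows criterion 2 also satisfies Section 10.2, so on this reading the section is incomplete rather than contradictory. That softens the point but does not remove it. Having referred to the requirement, Section 10.2 attaches its own, shorter time limit, and a reader of that section alone would not learn of the remaining period.

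The second defence is that any practical effect depends on the consent form, which Section 10.2 says is supplied separately. That stands. The form may carry the 3 months, and the protocol does not say which of its sections the form was drafted from. No woman has been shown to be told the wrong period.

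Third, 53 to 60 days is close to the worst case under footnote p. This also stands: completers last treated by Month 9 have no nominal gap, and Section 5.6.2 keeps patients who stop treatment without starting a prohibited one in follow-up to the final visit, so many early stoppers have none either. The range also depends on which visit window is used, as shown in the sensitivity figures.

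Last, the protocol gives no expected number of women of childbearing potential, so any statement about how many are affected is a judgement.

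**Conclusion.** The point holds, at minor severity. Section 10.2 gives a shorter contraception period than criterion 2, and the protocol's own schedule makes the difference real: about 53 to 60 days after a last treatment at Month 11, about 30 days for a completer last treated at Month 10, and none at Month 9 or earlier. The main figure assumes that 3 months means 90 days and that the end-of-study visit is timed by footnote p.

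Within criterion 2 the explicit 3-month sentence should be taken as governing. The opening clause, "unless they are using effective methods of contraception during dosing study treatment", is only loosely worded.

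The conclusion is about the protocol text and makes no claim about the consent form. Only women of childbearing potential are concerned, probably few of the at least 56 patients to be randomized, though that is an assumption. Endpoints, error rate, sample size and analyses are not touched.

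**What to change.** In Section 10.2, replace the time limit in the sentence on women of childbearing potential with the period from criterion 2: the whole study plus 3 months after study treatment discontinuation. Reword the opening clause of criterion 2 so that it gives the same period and not just the dosing phase. Then check that the model consent form states that period too.

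The cost is wording in two protocol sentences and one check of the consent form. No visits, patients or analyses are added.

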## **10.3 Responsibilities of the investigator and IRB/IEC**

Before initiating a trial, the investigator/institution must obtain approval/favorable opinion from the Institutional Review Board/Independent Ethics Committee (IRB/IEC) for the trial protocol, written informed consent form, consent form updates, subject recruitment procedures (e.g., advertisements) and any other written information to be provided to patients/subjects. Prior to study start, the investigator is required to sign a protocol signature page confirming his/her agreement to conduct the study in accordance with these documents and all of the instructions and procedures found in this protocol and to give access to all relevant data and records to Novartis monitors, auditors, Novartis Quality Assurance representatives, designated agents of Novartis, IRBs/IECs, and regulatory authorities as required. If an inspection of the clinical site is requested by a regulatory authority, the investigator must inform Novartis immediately that this request has been made.

## **10.4 Publication of study protocol and results**

Novartis assures that the key design elements of this protocol will be posted in a publicly accessible database such as [clinicaltrials.gov](http://clinicaltrials.gov). In addition, upon study completion and finalization of the study report the results of this trial will be either submitted for publication and/or posted in a publicly accessible database of clinical trial results.

## 10.5 Quality Control and Quality Assurance

Novartis maintains a robust Quality Management (QM) system that includes all activities involved in quality assurance and quality control, including the assignment of roles and responsibilities, the reporting of results, and the documentation of actions and escalation of issues identified during the review of quality metrics, incidents, audits and inspections.

Audits of investigator sites, vendors, and Novartis systems are performed by Novartis Pharma Auditing and Compliance Quality Assurance, a group independent from those involved in conducting, monitoring or performing quality control of the clinical trial. The clinical audit process uses a knowledge/risk based approach.

Audits are conducted to assess GCP compliance with global and local regulatory requirements, protocols and internal SOPs, and are performed according to written Novartis processes.

## 11 Protocol adherence

This protocol defines the study objectives, the study procedures and the data to be collected on study participants. Additional assessments required to ensure safety of patients should be administered as deemed necessary on a case by case basis. Under no circumstances is an investigator allowed to collect additional data or conduct any additional procedures for any research related purpose involving any investigational drugs under the protocol.

Investigators ascertain they will apply due diligence to avoid protocol deviations. If an investigator feels a protocol deviation would improve the conduct of the study this must be considered a protocol amendment, and unless such an amendment is agreed upon by Novartis and approved by the IRB/IEC and health authorities, where required, it cannot be implemented.

### 11.1 Protocol amendments

Any change or addition to the protocol can only be made in a written protocol amendment that must be approved by Novartis, health authorities where required, and the IRB/IEC prior to implementation. Only amendments that are intended to eliminate an apparent immediate hazard to patients may be implemented immediately provided the health authorities are subsequently notified by protocol amendment and the reviewing IRB/IEC is notified. Notwithstanding the need for approval of formal protocol amendments, the investigator is expected to take any immediate action required for the safety of any patient included in this study, even if this action represents a deviation from the protocol. In such cases, the reporting requirements identified in [Section 7](#) Safety Monitoring must be followed.

### 13 Appendix 1: Clinically notable vital signs

The criteria for clinically notable abnormal vital signs are shown below. In order to be identified as being potentially clinically notable abnormal, an on-treatment vital signs value would need to meet the criterion value, and represent a change of at least the magnitude noted in the change column.

#### Clinically notable abnormal vital signs values for adults

Variable	Criterion Value	Change Relative to Baseline
Heart Rate	≥ 120 b.p.m. ≤ 50 b.p.m.	increase of ≥ 15 b.p.m. decrease of ≥ 15 b.p.m.
Systolic blood pressure	≥ 180 mm Hg ≤ 90 mm Hg	increase of ≥ 20 mm Hg decrease of ≥ 20 mm Hg
Diastolic blood pressure	≥ 105 mm Hg ≤ 50 mm Hg	increase of ≥ 15 mm Hg decrease of ≥ 15 mm Hg

## **14 Appendix 2: Pre-Injection procedures for ranibizumab**

The following procedures (except where noted) will be conducted by the injecting physician to assure aseptic conditions:

1. Before treatment, the patients should be instructed to self-administer antimicrobial drops four times daily for three days prior to treatment.
2. Patients should be sufficiently anesthetized and administered with broad-spectrum antimicrobial eye drops before ranibizumab administration.
3. Intravitreal injection of ranibizumab should be conducted under aseptic conditions:
  - The technician assembles the supplies and prepares a sterile field. Supplies include swabs, sterile surgical gloves, sterile pads, pack of sterile cotton-tipped applicators, eyelid speculum, sterile ophthalmic drape, topical anesthetic, disinfectant ophthalmic solution, subconjunctival anesthetic, ophthalmic broad spectrum antimicrobial solution, and injection supplies.
  - The physician is to perform surgical hand and finger disinfection and use sterile gloves.
  - Disinfect the periocular skin and eyelid of the study eye in preparation for injection. Scrub the eyelid, lashes, and periorbital skin with disinfectant ophthalmic solution swabs, starting with the eyelid and lashes and continuing with the surrounding periocular skin. Make certain that the eyelid margins and lashes are swabbed, and proceed in a systematic fashion, from medial to temporal aspects.
  - Place a sterile ophthalmic drape to isolate the field, and place the sterile speculum underneath the eyelid of the study eye.
  - Sterilize the conjunctiva sac of the study eye according to local practice, making sure the planned injection site on the conjunctiva has been disinfected.
  - Use a sterile pad in a single wipe to absorb excess liquid and to dry the periocular skin.
4. Instruct patient to direct gaze away from syringe prior to ranibizumab injection.

